9.10 Expected Adverse Events

As with any endovascular intervention, TAVI involves some risks and possible complications. The following anticipated events have been identified as possible complications of TAVI procedures:

- Acute cardiovascular surgery (need for)
- Acute coronary artery occlusion
- Acute myocardial infarction
- Acute neurological events such as stroke, transient ischemic attack (TIA), and encephalopathy
- Allergic reaction to contrast, antiplatelet therapy or device component materials
- Angina pectoris
- Anesthesia reactions
- Aneurysm or pseudoaneurysm
- Arteriovenous fistula
- Ascending or descending aorta trauma
- Atrial or ventricular arrhythmias or fibrillation or sustained heart palpitations requiring therapy
- Bleeding complications such as hematoma and hemorrhage
- Blood loss requiring transfusion
- Bowel ischemia
- Coronary artery or other vascular injury, dissection, or perforation (which may require repair)
- Embolism (air, tissue, device, or thrombus)
- Fever
- Femoral nerve damage
- Hemodynamic changes
- Hypertension or hypotension (sustained requiring therapy)
- Infection, including endocarditis and septicemia
- Pain (at the femoral puncture site, abdominal, back, or other)
- Percutaneous coronary intervention (need for)
- Peripheral ischemia, peripheral nerve damage

- Pulmonary edema
- Pyrogenic reaction
- Renal complications, injury, or failure
- Unstable angina
- Vascular complications which may require vessel repair
- Vessel spasm (sustained, not responding to therapy)

In addition to the risks listed above, the potential risks specifically associated with the TriGuard HDH or TriGUARD 3 procedure include, but may not be limited to, the following:

- Dissection of the innominate artery by improper manipulations, disruption or migration of the TriGuard HDH CEPD filter due to passage of other instrumentation, e.g.: balloon, stent, catheter, wire
- Blue toe syndrome or blue discoloration of a toe
- Femoral bleeding at the access site
- Local trauma to the aortic wall due to device migration

10.0 Risk/Benefit Analysis

10.1 Potential Risks and Discomforts

Enrollment in the trial involves exposure to some risks. Most risks of trial participation are not materially different than those encountered by an individual undergoing TAVI outside the context of the trial (§9.10). However, the use of the TriGuard HDH or TriGUARD 3 embolic protection devices may involve exposure to additional risks (§9.10) as well as other potential risks of an unknown nature.

10.2 Methods to Minimize Risks

The clinical investigation plan is specifically designed to manage and minimize risks through careful subject selection, thorough training of investigators, adherence to pre-determined time points to assess subject clinical status, and regular clinical monitoring visits by Sponsor-appointment monitoring personnel. A dedicated contract research organization has been included in the study team to ensure high quality follow-up and minimize potential drop out. In addition, an independent Data Safety Monitoring Committee will monitor the safety of subjects throughout the trial.

10.3 Potential Benefits

The targeted trial population (subjects with severe symptomatic AS meeting indications for TAVI) has been demonstrated to be at risk for stroke and other neurological complications during and after the procedure. The study intervention has the potential to benefit subjects by preventing or reducing cerebral embolization during the TAVI procedure, limiting subsequent cerebral ischemia. Potential risks and benefits will be evaluated on an individual basis and discussed with each patient prior to enrollment in the study.

11.0 Study Committees

11.1 Patient Review Committee (PRC)

The PRC will ensure appropriate and consistent application of selected anatomic eligibility criteria to all potentially eligible subjects at all study sites. The PRC will consist of at least one imaging specialist, two interventional cardiologists, and a Sponsor representative (non-voting role).

Following initial pre-screening for study eligibility by the research team and documentation of informed consent, the following information will be submitted to the PRC for review for each potentially eligible subject:

- A completed Screening Worksheet
- The results of independent core laboratory analysis of CT imaging (standard and contrast-enhanced angiography preferred) of the left heart, aorta, great vessels, and peripheral access vessels performed up to 1 year prior to procedure.

The PRC will meet regularly during the enrollment phase to determine whether potential candidates meet selected applicable anatomic eligibility criteria (§6.1.2.1.15, §6.1.2.1.16, §6.1.2.1.17, §6.1.2.1.18, §6.1.2.1.19). PRC responsibilities, membership, meeting frequencies, and procedures will be outlined in the PRC charter prior to the onset of the trial.

11.2 Clinical Events Committee (CEC)

The CEC will be responsible for adjudicating all site-reported cardiovascular events and all adverse events potentially meeting endpoint criteria, in an ongoing fashion during the trial. In order to fully capture all endpoints, events potentially meeting end-point criteria will be considered an SAE (even if they do not result in death or prolong the hospitalization) and sent to the medical monitor for further assessment. Events appropriately classified as potential endpoints by the medical monitor will be sent to CEC for adjudication.

Events potentially meeting end-point criteria and therefore defined as SAE for this purpose include:

- Death
- Stroke/TIA or any other Neurological Dysfunction (NeuroARC definitions)
- MI or Coronary artery obstruction requiring intervention
- Bleeding (including life-threatening or disabling bleeding, Major and Minor bleeding)
- Acute kidney injury (stage 2 or 3 or requiring dialysis)
- Major vascular complications
- Valve-related dysfunction requiring repeat procedure

The CEC will include at least one interventional cardiologist with relevant clinical experience and one neurologist with experience in clinical trials involving stroke who are otherwise independent of the Sponsor or the conduct of the study. Members will not have scientific, financial or other conflicts of interest related to Keystone Heart Ltd. or the Investigators. The CEC will operate and conduct all meetings and event reviews independent of the Sponsor unless specific expert knowledge regarding the characteristics or function of the study device is requested by the CEC from the Sponsor.

The CEC will meet regularly throughout the study to adjudicate events in an ongoing and timely fashion. The adjudication process, event definitions and required source document materials for each type of event will be pre-specified in the CEC Charter prior to the onset of the trial. The adjudication process will include CEC member review of copies of all relevant medical records and imaging studies associated with an event reporting. All adjudication decisions will be made by the CEC in an independent fashion based upon review of all available medical evidence associated with an event.

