Patient population:	The study will enroll up to 603 subjects (499 randomized subjects and up to 104 roll-in subjects) meeting approved indications for transcatheter aortic valve implantation. Of these, up to 295 will be randomized in Phase II, with an additional 40-50 roll in patients.
Patient Follow-Up:	
Phase I: All subjects were followed clinically in-hospital and at 30 and 90 days, underwent diffusion-weighted MR imaging 2 to 5 days post-procedure, and underwent neurologic and neuropsychological testing pre-procedure, post-procedure (2-5 days post-procedure), and at 30 and 90 days.
 
Phase II: All subjects will be followed clinically in-hospital and at 30 days, undergo diffusion-weighted MR imaging 2 to 5 days post-procedure, and undergo neurologic testing pre-procedure, post-procedure (2-5 days post-procedure), and at 30 days. 90 days phone-call follow-up will assess the occurrence of death and/or stroke.

Study Committees:	
Patient Review Committee
 
A Patient Review Committee (PRC) will evaluate each potentially eligible subject (Includes confirmation that subject meets selected anatomic eligibility criteria based on imaging analysis by an independent CT core laboratory). All subjects must be approved by the PRC prior to enrollment in the trial.
 
Clinical Events Committee
 
An independent Clinical Events Committee (CEC) will adjudicate all site-reported cardiovascular adverse events and all site-reported adverse events potentially meeting endpoint criteria, in an ongoing fashion during the trial. In the Intervention and Roll-In groups, relationship to the investigational device or investigational procedure will also be adjudicated.
 
Data and Safety Monitoring Board
 
An independent Data and Safety Monitoring Board (DSMB) will be responsible for the oversight and safety monitoring of the study. The DSMB will advise the Sponsor regarding the continuing safety of the trial subjects and those yet to be recruited to the trial, as well as the continuing validity and scientific merit of the trial.

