--	---

Blinding	
This is a single-blind study. The following individuals will be blinded to the subject's treatment allocation:
 
 • Subject and his/her family members • Site personnel administering neurological evaluations (NIHSS or mRS and/or neuropsychological test battery in Phase I); these individuals will also be blinded to DW-MRI results • Members of the Data and Safety Monitoring Board • MRI Core Laboratory personnel performing imaging analysis 
Un-blinding will occur only after the database has been locked for the analysis of the primary endpoint or to protect subject rights, welfare, or well-being at the request of the DSMB.

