6.3 Blinding

This is a single-blind study. The following individuals will be blinded to the subject's treatment allocation:

- Subject and his/her family members
- Site personnel administering neurological evaluations (NIHSS and mRS); these individuals will also be blinded to DW-MRI results
- Members of the Data Safety Monitoring Committee
- MRI Core Laboratory personnel performing imaging analysis

Un-blinding will occur only after the database has been locked for the analysis of the primary endpoint or to protect subject rights, welfare, or well-being at the request of the DSMB. The circumstances under which the DSMB may request unblinding to treatment allocation will be outlined in the DSMB charter prior to the onset of the trial.

If a site investigator determines it is necessary to reveal treatment allocation to the subject as a result of complication or injury, he or she is requested to notify the Sponsor.

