- A full neurological evaluation should be performed by a neurologist in all patients in whom a stroke or TIA is suspected on the basis of the NIHSS, mRS, or other signs or symptoms.
- A neuropsychological test battery (§16.7) will be administered 2 to 5 days (≥ 48 to < 144 hours) post-procedure by a qualified individual. The test battery includes: (Phase I only).
 - Montreal Cognitive Assessment (MoCA)
 - Repeatable Battery for the Assessment of Neuropsychological Status (RBANS)
 - Trail Making Test Parts A and B

Prior to hospital discharge, research staff should also review the follow-up requirements with the subject to help ensure that the patient returns to the clinic for the one-month follow-up visit. Telephone numbers should be obtained from the patient to ensure the ability to contact him or her at the required time. These phone numbers should include all home numbers, work numbers and primary physician numbers. A phone number of a relative or friend should also be requested.

Note: All clinically significant adverse events should be carefully documented by the research staff using the adverse event data forms. Any clinically-indicated neuroimaging should be forwarded to the MRI Core Laboratory.

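### As written, the committee that classifies strokes for Tier 1 of the primary efficacy endpoint is not listed as blinded, and no masking of its case packets is specified

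*Combined protocol and SAP*

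**What the plan says.** Section 6.3 opens: "This is a single-blind study. The following individuals will be blinded to the subject's treatment allocation". Four roles follow: the subject and family, the site staff who administer the NIHSS and mRS, "Members of the Data Safety Monitoring Committee", and the MRI core laboratory. The Blinding entry in the synopsis gives the same four, ending with "MRI Core Laboratory personnel performing imaging analysis". The CEC is in neither list.

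Section 11.2 sets out the committee's task: "The CEC will be responsible for adjudicating all site-reported cardiovascular events and all adverse events potentially meeting endpoint criteria". Death, stroke, TIA and other neurological dysfunction are among the events it names. On materials it says: "The adjudication process will include CEC member review of copies of all relevant medical records and imaging studies associated with an event reporting". No redaction is mentioned. The medical monitor screens events before they reach the committee, and the committee may ask the sponsor for expert knowledge about the device. The adjudication process, event definitions and source documents are left to a CEC Charter.

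On relatedness, the synopsis (Study Committees) says: "In the Intervention and Roll-In groups, relationship to the investigational device or investigational procedure will also be adjudicated". Section 5.4.2.1.2 and the synopsis list of secondary safety endpoints assign this task to the same committee, for all safety endpoints and for those two groups only.

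Section 7.5 adds: "A full neurological evaluation should be performed by a neurologist in all patients in whom a stroke or TIA is suspected". It does not say whether that neurologist is one of the blinded raters.

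**The concern.** Operators and site investigators know the allocation by design. Masked central classification is therefore the main protection left for a stroke call. The plan blinds the NIHSS raters (Tier 2) and the MRI readers (Tiers 3 and 4), but specifies no such protection for the tier that is compared before them.

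Stroke calls need judgement. The VARC-2 definition in Appendix I allows diagnosis on clinical grounds alone, requires other causes to be ruled out, and excludes non-focal encephalopathy unless imaging clearly shows infarction. If adjudicators know who had the device, borderline calls could differ by arm, in either direction.

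The calls feed Tier 1 of the primary efficacy endpoint (5.4.1.1.2), the first and third gated secondary endpoints (all stroke at 7 days, and death or stroke at 7 days; 5.4.2.1.1), and the stroke component of the primary safety composite (5.4.1.1).

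**Working it through.** **1. Is the CEC masked on the text?**
- It is absent from both lists, although another independent committee, the DSMB, is named in each.
- Section 6.3 and Section 11.3 send the DSMB's unblinding rules to the DSMB charter. Section 11.2 lists what the CEC Charter will contain, and blinding is not among the items.
- The relatedness task is limited to device-treated groups, so the committee must learn allocation for that task. Nothing states that event classification comes first or is locked.
- Independence from the sponsor, which Section 11.2 requires, deals with conflict of interest. It is not masking.

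**2. How much of the primary endpoint is exposed?** Inputs from Section 12.2.4.1.2: Tier 1 rates of 11% (control) and 6% (device), with 75 and 150 subjects.
- Pairs with at least one Tier 1 event: 1 − (0.89 × 0.94) = 0.163, about 16%.
- Control event only: 0.11 × 0.94 = 10.3%. Device event only: 0.89 × 0.06 = 5.3%. Both: 0.11 × 0.06 = 0.7%. Event day matters only in the last group.
- Expected Tier 1 events: 75 × 0.11 = 8.25 controls and 150 × 0.06 = 9 device subjects. Both counts include deaths.

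**3. Illustration on the Tier 1 rate.** The documents give no misclassification rate, so the counts below are assumptions.

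| Device-arm strokes not confirmed | Device Tier 1 rate |
|---|---|
| 0 | 9/150 = 6.0% |
| 1 | 8/150 = 5.3% |
| 2 | 7/150 = 4.7% |
| 3 | 6/150 = 4.0% |

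**4. Illustration on the primary test.** The Finkelstein-Schoenfeld test was simulated at one-sided 0.025, using the Table 11b rates, the 15% or 50 mm³ win threshold, and 15% MRI and 5% other missing data. Event days and the spread of volumes within each bin had to be assumed. With the plan's 30% volume reduction applied, power was 87.6% (150 v 75) and 96.2% (150 v 138). These agree with the stated figures of more than 80% and at least 92%. Without that reduction they were 61% and 76%.

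The simulation was then run with no true effect on any tier, a true Tier 1 rate of 11% in both arms, and a lower recorded device rate (2,000 runs per cell):

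| Recorded device rate | Events lost of 16.5 | Type I error, 75 controls | Type I error, 138 controls |
|---|---|---|---|
| 11% | 0 | 2.3% | 2.5% |
| 9% | 3 | 4.7% | 5.0% |
| 7.5% | 5.25 | 6.1% | 7.6% |
| 6% | 7.5 | 9.3% | 11.1% |

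These are probably overstatements. Subjects whose stroke was not confirmed were given ordinary Tier 2 to 4 outcomes, whereas real ones would often show NIHSS worsening or lesions. The last row would discard 7.5 of 16.5 events, some of them deaths, and is an extreme.

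**5. Pooled Phase I controls.** 63 × 0.11 = 6.9, so about 7 Tier 1 events could enter the primary comparison from Phase I.

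**The case against.** A reader might infer that stroke is adjudicated open-label, or that the CEC must know allocation when it classifies a stroke. The documents support neither. No section calls the committee unblinded. Section 11.2 leaves process and source materials to an unseen charter, which could specify masking. Relatedness is an additional judgement that can be made after classification. What stands is narrower: neither the blinding sections nor Section 11.2 requires masking or that order.

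It might also be said that Tier 1 dominates the endpoint. On the plan's rates about 84% of pairs contain no Tier 1 event and pass to tiers read by blinded staff. Tier 1 also includes all-cause death, where occurrence leaves little to judgement.

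The definition limits discretion too. A deficit under 24 hours counts as a stroke if available imaging shows a new infarct, and clinically indicated neuroimaging goes to the MRI core laboratory. The plan expects lesions in 73% of device and 89% of control subjects who reach Tier 3, so a TIA label will often be unavailable. Even so, the committee must still decide whether a sign is a qualifying deficit and whether another cause explains it, and the plan expects 15% of MRIs to be missing. A stroke that is not confirmed is also not a win: the pair moves on to Tier 2 and then to MRI.

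The neurologist who does the full work-up may be the blinded rater. The text is ambiguous and does not show a gap.

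**Conclusion.** The point holds in this form: as written, the CEC is on neither blinding list, no masking of its packets is specified, and one committee both classifies stroke from the full record and judges relatedness in device-treated subjects only. Unless the charter separates these tasks, the stroke calls and event day in Tier 1, the two gated secondary endpoints and the stroke part of the safety composite are open to allocation-aware adjudication.

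The share of pairs exposed is at most about 16%, because that figure includes deaths. Event day matters in under 1% of pairs. The size and direction of any bias are unknown. The shift from 6.0% to between 5.3% and 4.0%, and the simulated type I error, rest on assumed counts of unconfirmed strokes; they show sensitivity and do not estimate bias. With so few expected events, a handful of calls matters, and the remedy is cheap, so the plan should be changed.

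**What to change.** Write a two-step process into Sections 6.3 and 11.2 and the CEC Charter:

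1. The CEC decides event occurrence, type and date from packets with allocation and device references redacted, and locks that decision.
2. Allocation is released only afterwards, for relatedness in Intervention and Roll-In subjects, and cannot reopen step 1.

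Add the CEC (step 1) to both blinding lists. State the blinding status of the medical monitor, who screens events first, and of the neurologist who does the full evaluation.

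If the 63 Phase I controls are pooled, put their potential stroke events through the same masked step. Otherwise the arms would be compared under different adjudication rules. About 7 Tier 1 events are expected there, deaths included; suspected events that were not confirmed also need review.

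The cost is wording, redaction work and re-review of a few Phase I events. Masking will sometimes be imperfect, for example when a bleed at the contralateral access site reveals device use. No extra subjects are needed, and the relatedness review is kept.

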11.3 Data and Safety Monitoring Board (DSMB)

The Data Safety Monitoring Committee (DSMB) is responsible for the oversight and safety monitoring of the study. The DSMB advises the Sponsor regarding the continuing safety of the trial subjects and those yet to be recruited to the trial, as well as the continuing validity and scientific merit of the trial. The DSMB will be composed of members who are leading experts in cardiovascular medicine, vascular neurology (with experience in clinical trials involving stroke), and biostatistics who are not participating in the trial and have no affiliation with the sponsor.

During the enrollment phase of the trial, the DSMB will review accumulating safety data to monitor for the incidence of serious adverse events that would warrant modification or termination of the trial according to a pre-specified safety monitoring plan. Any DSMB recommendations for study modification or termination prompted by concerns regarding subject safety or issues relating to data monitoring or quality control will be submitted in writing to the Sponsor for consideration and final decision. However, if the DSMB at any time determines that a potential serious risk exists to subjects in this trial, the DSMB chairman will immediately notify the Sponsor.

The DSMB will meet at regular intervals to review the safety data. DSMB responsibilities, membership, meeting frequencies, and procedures will be outlined in the DSMB charter prior to the onset of the trial. The circumstances under which the DSMB may request unblinding to treatment allocation will also be outlined in the charter.

12.0 Statistical Considerations and Analysis Plan

12.1 General Analysis Definitions

Analysis will be conducted using SAS (version 9.3 or greater), unless otherwise noted. Descriptive statistics for continuous variables will include mean, median, standard deviation, quartiles, minimum, maximum, and sample size for each treatment group. Binary variables will be summarized using frequencies, percentages, and sample size for each treatment group. For time-to-event data, Kaplan-Meier estimates at the indicated time points will be displayed graphically. Further clarifications regarding endpoint criteria assessment and analysis between subjects will be provided in the Statistical Analysis Plan (SAP).

12.1.1 Adaptive Design

Once at least 50% of the initial randomized Phase II cohort has been enrolled and has reached the 30 day primary efficacy endpoint evaluation time point, the independent unblinded statistician will perform a conditional power analysis. If the trial, based on the results at that point is either $\leq 40\%$ powered to achieve success in meeting the primary efficacy endpoint or is $\geq 80\%$ powered to achieve the primary efficacy endpoint no sample size reestimation will be required. If the conditional power of the study is $>40\%$ but $<80\%$ the independent unblinded statistician will recommend a sample size reestimation, subject to approval by the Sponsor. If this analysis determines that more than 225 randomized subjects

will be required to ensure adequate study power, enrollment may continue until the required number of subjects have been enrolled, or until the total subject limit for the study has been reached (whichever occurs first).

Promising zone computation

After the trial has enrolled 50% of the originally planned sample size of the initial randomized cohort (112 patients), an independent statistician will estimate all 4 levels of the Finkelstein-Schoenfeld hierarchy for device and control, and use these estimates to re-calculate the trial's power given the originally planned 225 Phase II patients.

If the trial power is between >40% and <80%, the trial will be considered promising and the trial will readjust the sample size to attain 80% power. If on the other hand the power falls to $\leq 40\%$ or $\geq 80\%$, the sample size will not be adjusted.

Conditional power computation

The conditional power will estimate all four Finkelstein-Schoenfeld levels and use these estimates to simulate future enrolled patients. The power simulation will follow exactly the same algorithm as used to power the original Phase II study with updated estimates of effect size.

Alpha spending and controlling type I error

Since the study leadership and sponsor do not conduct any formal statistical hypothesis test, this design will not incur any alpha penalty or affect the overall type I error. As detailed by Mehta and Pocock¹¹ and based on the work of Chen¹⁰ as long as the sample size reestimation occurs only when the conditional power falls in the promising zone, no additional alpha spend is required and the overall type I error is preserved.

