12.2.1.1.2 Primary Efficacy Hypothesis

The primary hypothesis is that TAVI with the TriGUARD 3 system is superior to standard (unprotected) TAVI for the primary hierarchical composite efficacy endpoint of all-cause mortality or any stroke at 30 days (Tier 1), NIHSS worsening from baseline assessed at 2-5 days post-procedure (Tier 2), freedom from any cerebral ischemic lesions detected by diffusion-weighted magnetic resonance imaging (DW-MRI) 2 to 5 days post-procedure (Tier 3), and total volume of post-procedure cerebral ischemic lesions detected by DW-MRI (Tier 4).

Specifically, the primary efficacy hypotheses are:

H_0 : The hierarchical composite of death/stroke, NIHSS worsening, freedom from any lesions detected by DW-MRI, and larger total lesion volumes is not different between Intervention and Control groups

H_1 : The hierarchical composite of death/stroke, NIHSS worsening, freedom from any lesions detected by DW-MRI, and larger total lesion volumes is lower in the Intervention group than in the Control group

The null hypothesis will be tested at the final analysis at a one-sided 0.025 level of significance. The null hypothesis will be tested using the chi-square test according to the method described in Finkelstein-Schoenfeld² and Pocock⁷⁷.

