To determine the required sample size, calculations were performed by simulating 5000 samples on SAS software postulating the above parameters; mortality and stroke rates and proportions of patients with NIHSS worsening, any MRI lesions and volumes divided to subsets were simulated by a random binary function.

An evaluable sample size of 225 subjects (2:1 randomization with 150 in the Intervention group and 75 new Control subjects) is sufficient to demonstrate superiority of the Intervention group to the Control group for the primary efficacy endpoint when pair-wise comparisons are made between subjects using the Finkelstein-Schoenfeld method,² and outcomes between treatment groups are compared by the chi-square test.

Therefore, the initial randomized cohort sample size of 225 subjects (150 in the Intervention group and 75 new control subjects) will have >80% power to demonstrate superiority of the Intervention group for the primary efficacy endpoint (one sided $\alpha=0.025$). Notably, in several simulations, considering different distributions for lesion volume and different distributions for death/ stroke, the study power remained greater than 80%.

Adding the 63 control subjects already enrolled in REFLECT Phase I for a total of 138 control subjects would increase the power to at least 92% to demonstrate superiority of the primary efficacy endpoint. 5% loss to follow up is included.

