The assumptions for powering the primary efficacy endpoint are based on neurologic, and imaging data from a limited number of subjects in the above mentioned RCTs (§12.2.2). In Phase I due to uncertainty regarding the primary efficacy endpoint, an unblinded interim analysis was planned to be conducted to re-evaluate the sample size required to demonstrate superiority of the Intervention group to the Control group. The unblinded interim analysis was planned to be conducted when 90 subjects total who meet the eITT population definition have completed the 30-day follow-up visit. This interim analysis was to be inspected by an independent data safety and monitoring Board (DSMB) and the unblinded results will not be made privy to the sponsor, investigator, or any REFLECT team member, even in the event of a DSMB recommendation of an increase in sample size (i.e., the sponsor will not be made privy to the reason for any DSMB recommendation of an increase in sample size). If the interim analysis would have determined that more than 285 randomized subjects will be required to ensure adequate study power, enrollment would have continued (contingent on DSMB recommendation and prior FDA approval, and at the Sponsor's discretion) until the required number of subjects would have been enrolled, or until the total subject limit for the study has been reached (whichever occurs first).

Specifically, at the interim analysis in Phase I, the trial sample size was to be re-calculated, if necessary, to ensure 80% conditional power to demonstrate superiority (overall 2-sided $\alpha=0.05$) of the Intervention group to the control group for the primary efficacy endpoint, conditioned on the interim unblinded results and loss to DW-MRI follow-up, according to the eITT population definition (there will be no imputation of missing data in this interim analysis; i.e., missing data will be excluded; also, sample size can only be increased at this interim

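### Phase II asks the Sponsor to approve a sample-size increase after the unblinded interim, without the DSMB step or the non-disclosure rule that Phase I had

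*Combined protocol and SAP*

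**What the plan says.** - **Who decides.** Section 12.1.1 (Adaptive Design) states that inside the 40–80% zone "the independent unblinded statistician will recommend a sample size reestimation, subject to approval by the Sponsor". The same condition appears in the synopsis (study design and adaptive design), in 5.2 and in 6.2.1. None of these places puts the DSMB between the statistician and the Sponsor, or says what the Sponsor is shown.
- **Whether the rule binds.** The promising-zone paragraph of 12.1.1 says "the trial will readjust the sample size to attain 80% power", which reads as automatic. The paragraph before it makes the increase a recommendation needing approval and uses permissive wording for continued enrolment.
- **What Phase I had.** Section 12.4.3 sent the Phase I interim to the DSMB and stated that "the unblinded results will not be made privy to the sponsor, investigator, or any REFLECT team member". It added that the Sponsor would not learn why an increase was recommended. A note at the end of that description refers Phase II readers to 12.1.1, which contains neither provision.
- **What is public.** The zone limits, the 80% target, the interim at 112 of 225 subjects and the limit of 295 randomized subjects all stand in the protocol.

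**The concern.** An unblinded interim is normally walled off from the party that runs the trial, because knowledge of the trend can influence conduct in ways the final test cannot correct. Here the Sponsor is handed a discretionary decision after the interim, and the request to decide carries information.

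The operators cannot be blinded, and some judgement steps remain after the interim. Whether Phase I controls are pooled is settled only at the primary analysis (12.4.3), and a medical monitor decides which events go to adjudication (11.2). The documents do not say that the Sponsor controls either step. Such steps are still a reason to keep interim knowledge narrow.

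**Working it through.** **1. The plan's own power figure.** Section 12.2.4.1.2 states that 225 subjects (150 vs 75) "will have >80% power to demonstrate superiority of the Intervention group for the primary efficacy endpoint", rising to at least 92% with 138 controls. A simulated Finkelstein-Schoenfeld test used the plan's tier rates, the 30% within-class volume reduction, 15% MRI loss, 5% other loss and the 15%/50 mm³ win rule. It gave 78–91% at 150 vs 75 and 89–97% at 150 vs 138. Two scenarios come close to both stated figures (82.2%/91.9% and 82.7%/92.7%). The documents do not give the following, so they were assumed: volumes uniform within class, a top of 500 to 3000 mm³ for the largest class, event days uniform over 0–30, and NIHSS worsening of 1–4 points. The stated power is reproducible, so effects giving 80% and 92% power at 225 are used below.

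**2. Inputs for reading N back.** One-sided alpha is 0.025 (12.2.1.1.2: "The null hypothesis will be tested at the final analysis at a one-sided 0.025 level of significance"), so the critical value is 1.960. The 80% target gives 0.842. The interim is at 112 of 225, a fraction of 0.498, with square root 0.7055. Section 12.1.1 supports two readings of the power calculation.

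**3. Reading A: power at 225 re-calculated from the interim estimate.**
- Interim z = (1.960 + z(power)) × 0.7055.
- Required N = 225 × [2.802 / (1.960 + z(power))]².
- Zone limits: 40% power gives z = 1.707 × 0.7055 = 1.20, and 80% gives 2.802 × 0.7055 = 1.98.
- Target 240 means power 77.4% and z = 1.91. Target 270 means 72.5% and 1.80. Target 294 means 68.8% and 1.73.
- Power of 68.7% needs exactly 295. Everything from 40% to 68.7% would need 295 to 606, so it appears as 295, with z anywhere from 1.20 to 1.73.

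**4. Reading B: conditional power under the current trend.** With t = 112/N, conditional power = 1 − Φ[(1.960 − √t·z)/√(1−t) − z·√((N−112)/112)].
- Zone limits: z = 1.26 and 1.80.
- Conditional power of 75% gives N = 254 (z = 1.72), 70% gives 283, and 68.0% gives 295 (z = 1.62).
- From 40% to 68.0% the required N runs from 520 down to 295, so the target is again 295, with z from 1.26 to 1.62.

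**5. How sharp the inference is.** A target of about 255 means z = 2.634 × 0.7055 = 1.86 under A but 1.72 under B, a gap of 0.14. If the simulation keeps the 5,000 samples of 12.2.4.1.2, its standard error at 75% power is √(0.75 × 0.25/5000) = 0.0061. Under A the target falls from 286.1 to 254.5 as power rises from 70% to 75%, or 6.3 subjects per percentage point. The noise is therefore about 0.61 × 6.3 ≈ 4 subjects. At (1.977 − 1.726)/70 ≈ 0.0036 in z per subject, that is about 0.014 for one standard error, or 0.03 for two.

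**6. How often each case arises.**

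| Effect | Reading | In zone | Of these, at 295 | Target 226–294 | No change |
|---|---|---|---|---|---|
| 80% power at 225 | A | 28.0% | 64.7% | 9.9% | 72.0% |
| 80% power at 225 | B | 19.6% | 63.2% | 7.2% | 80.4% |
| 92% power at 225 | A | 22.5% | 61.3% | 8.7% | 77.5% |
| 92% power at 225 | B | 15.2% | 60.7% | 6.0% | 84.8% |
| None | A | 9.0% | 79.9% | 1.8% | 91.0% |
| None | B | 6.9% | 74.8% | 1.7% | 93.1% |

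An increase thus tells the Sponsor at least that power is between 40% and 80%. Section 12.1.1 does not say whether the Sponsor receives the capped target or the uncapped requirement. The uncapped figure would extend the back-calculation over the whole zone.

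**The case against.** A reader might infer that the new N reveals the interim effect almost exactly. It does not. Most increases land on 295, which gives only a range, and no change means only that power was at most 40% or at least 80%. Even a target of 226–294 is blurred by the two readings, by simulation noise and by silence on whether Phase I controls enter the interim. N also yields one overall statistic, not the four tier effects.

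A reader might also infer that the firewall is lost. The Phase II text is silent; it does not permit disclosure. Section 6.3 restricts unblinding to after database lock or a DSMB request, and the DSMB charter is not among the documents. Phase I, too, left the increase to the Sponsor's discretion under a printed zone (50–80%) and target, so its new N could also have been read back. All of this stands. It does not close the gap, because 6.3 concerns subjects' treatment allocation and cannot be exhaustive when 12.1.1 provides for an unblinded statistician before lock. What Phase I had and Phase II lacks is the DSMB step and the stated non-disclosure.

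The Sponsor's other roles add nothing. Proctoring is described for roll-in cases only. The Patient Review Committee seat is non-voting and concerns eligibility before randomization. The final say on DSMB recommendations (11.3) covers safety, data monitoring and quality control.

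Finally, subjects, neurological assessors and the MRI core laboratory are blinded, and an independent committee adjudicates events. These limit the harm, and no actual bias is shown.

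**Conclusion.** The point holds as a gap in the Phase II interim procedure. The Sponsor takes a discretionary decision after an unblinded analysis, with no stated limit on what it learns, and 12.1.1 is inconsistent on whether the increase is automatic.

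Any approval request discloses the 40–80% zone. A target of 226–294 narrows the interim z to somewhere in about 1.6–2.0 overall (1.73–1.98 under reading A, 1.62–1.80 under B) and more closely within one reading. A target of 295 gives about 1.2–1.7. The narrower disclosure has a probability of about 6–10% under effects giving 80–92% power and about 2% under no effect.

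These figures assume a normal approximation, 2:1 allocation kept throughout, new controls only, and that the capped target is what is passed on. The documents do not show that the Sponsor would know the treatment effect or that alpha is inflated. This is a cheap improvement, worth making before the interim.

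**What to change.** - In 12.1.1, 5.2, 6.2.1 and both places in the synopsis, replace Sponsor approval after the interim with written Sponsor approval, given beforehand, for any increase up to the existing limit of 295.
- Make the zone rule binding, and remove the conflict in 12.1.1 between the recommending and the automatic wording.
- Have the independent statistician report to the DSMB. Pass only an enrolment instruction to those running enrolment: at most the capped target, never the uncapped requirement, conditional power or effect estimates.
- Restate for Phase II the 12.4.3 rule that the Sponsor, investigators and trial team see neither the unblinded results nor the reason for an increase.

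The cost is protocol and charter wording, with no subjects beyond 295 and no change to alpha. The Sponsor must plan for up to 295 in advance. Continuing past 225 will still show that the result fell in the promising zone, which this change cannot prevent.
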